8.8.2. Permitted Medications

Other than the prohibited medications and vaccines listed in Section 8.8.1, treatment with concomitant medications is permitted during the study. If there is any question regarding whether a concomitant medication may be used during the study, the study site should contact the medical monitor. Any medications used by the study subject should be captured in the concomitant medication eCRF.

9. STUDY SCHEDULE OF EVENTS AND PROCEDURES

9.1. Schedule of Events

In light of the public health emergency related to COVID-19, the continuity of clinical study conduct and oversight may require implementation of temporary or alternative mechanisms. Examples of such mechanisms may include, but are not limited to, any of the following: phone contact, virtual visits, telemedicine visits, online meetings, non-invasive remote monitoring devices, use of local clinic or laboratory locations, and home visits by skilled staff. Additionally, no waivers to deviate from protocol enrollment criteria due to COVID-19 will be granted. All temporary mechanisms utilized, and deviations from planned study procedures in response to COVID-19 are to be documented as being related to COVID-19 and will remain in effect only for the duration of the public health emergency.

Table 3: Schedule of Events for Arms 1, 2, 3, and 6a (Enrollment Wave 1) and Arms 7, 8, and 6c (Enrollment Wave 3)

Visit Period	Screening/Baseline				Vaccine Response Assessment				Follow-Up			Unscheduled Visit	ET		
Study Day	-21 to 1				15 ¹	29	43 ¹	57	71	183	267	380			
	Screening	Pre-dose	Dose ¹	Post-Dose											
Days After the First Vaccine Dose					14	28	42	56	71	168	252	365			
Window (day)					-1 to +3	±2	-1 to +3	±2	±2	±7	±14	±14			
Screening/Baseline and Key Laboratory Testing															
Inclusion/exclusion	X	X													
Informed consent	X														
Informed consent for optional FBR sub-study ²	X														
Informed consent for optional PGx sub-study ²	X														
Medical history	X														
Demographics	X														
Height and weight	X														
Pregnancy test (WOCBP) ³	X ³	X ³			X		X						X		
SARS-CoV-2 rapid (local/POC) RT-PCR ⁴	X ⁴	X ⁴			X ⁴	X ⁴	X ⁴	X ⁴	X ⁴	X ⁴	X ⁴	X ⁴	X ⁴		
SARS-CoV-2 rapid serology ⁵	X ⁵	X ⁵													
SARS-CoV-2 serology (central lab) ⁵	X ⁵													X	
Enrollment Wave and Treatment Assignment															
Site-managed assignment ⁶	X ⁶														
Randomization ⁶		X ⁶													
Study Drug and Vaccine Administration															
REGN10933+REGN10987 (arms 1, 2, 3, 7, and 8 only) ⁷			X ⁷												
Moderna mRNA-1273 vaccine (arms 1, 2, 3, 7, 8, 6a, and 6c) ⁷				X ⁷			X ⁷								
Biomarkers															
Serum for SARS-CoV-2 neutralization ⁸			X			X	X	X	X	X	X	X	X	X	
Serum for serology characterization ⁸	X				X	X	X	X	X	X	X	X	X	X	
Whole blood for PBMCs ⁸	X				X	X	X	X	X	X	X	X	X	X	
Serum for exploratory research	X				X	X	X	X	X	X	X	X	X	X	
Plasma for exploratory research	X				X	X	X	X	X	X	X	X	X	X	
Safety															
Vital signs ⁹	X	X ⁹		X ⁹	X ⁹		X ⁹								
Adverse events ¹²	X	X	X	X	X	X	X	X	X	X	X	X	X	X	
Concomitant medications	X	X	X	X	X	X	X	X	X	X	X	X	X	X	
Targeted physical examination	X														
Laboratory Testing (Central Lab)															
Hematology			X			X		X		X	X		X	X	
Blood Chemistry		X			X		X		X	X			X	X	
Urinalysis		X												X	
Drug concentrations and Immunogenicity															
Drug concentration (PK) sample ¹⁰			X ¹⁰		X ¹⁰	X	X	X	X	X	X				
Immunogenicity (ADA) sample ¹¹			X ¹¹			X					X				
Pharmacogenomics (Optional)															
Whole Blood for DNA			X ²												
Vaccine Booster Sub-Study (Optional)¹³															
Informed consent for vaccine booster sub-study ²														Refer to Table 6.	

Visit Period	Screening/Baseline				Vaccine Response Assessment				Follow-Up			Unscheduled Visit	ET	
	-21 to 1				15 ¹	29	43 ¹	57	71	183	267	380		
Study Day	Screening	Pre-dose	Dose ¹	Post-Dose										
Days After the First Vaccine Dose					14	28	42	56	168	252	365			
Window (day)					-1 to +3	±2	-1 to +3	±2	±2	±7	±14	±14		
Sample collection and assessments														

Table 4: Schedule of Events for Arms 4, 5, and 6b (Enrollment Wave 2)

Visit Period	Screening/Baseline				Vaccine Response Assessment			Follow-Up			Unscheduled Visit	ET	
	Study Day	-21 to 1			15	29 ¹	43	57	169	253	366		
Days After the First Vaccine Dose		Screening	Pre-dose	Dose ¹	Post-Dose	14	28	42	56	168	252	365	
Window (day)						±2	-1 to +3	±2	±2	±7	±14	±14	
Screening/Baseline and Key Laboratory Testing													
Inclusion/exclusion	X	X											
Informed consent	X												
Informed consent for optional FBR sub-study ²	X												
Informed consent for optional PGx sub-study ²	X												
Medical history	X												
Demographics	X												
Height and weight	X												
Pregnancy test (WOCBP) ³	X ³	X ³				X ³						X	
SARS-CoV-2 rapid (local/POC) RT-PCR ⁴	X ⁴	X ⁴			X ⁴	X ⁴	X ⁴	X ⁴	X ⁴	X ⁴	X ⁴		
SARS-CoV-2 rapid serology ⁵	X ⁵	X ⁵											
SARS-CoV-2 serology (central lab) ⁵		X ⁵										X	
Enrollment Wave and Treatment Assignment													
Site-managed assignment ⁶	X ⁶												
Randomization ⁶		X ⁶											
Study Drug and Vaccine Administration													
REGN10933+REGN10987 (arms 4 and 5 only) ⁷				X ⁷									
Moderna mRNA-1273 vaccine (arms 4, 5, and 6b) ⁷				X ⁷		X ⁷							
Biomarkers													
Serum for SARS-CoV2 neutralization ⁸		X			X	X	X	X	X	X	X	X	
Serum for serology characterization ⁸	X				X	X	X	X	X	X	X	X	
Whole blood for PBMCs ⁸	X				X	X	X	X	X	X	X	X	
Serum for exploratory research	X				X	X	X	X	X	X	X	X	
Plasma for exploratory research		X			X	X	X	X	X	X	X	X	
Safety													
Vital signs ⁹	X	X ⁹			X ⁹		X ⁹						
Adverse events ¹²	X	X	X	X	X	X	X	X	X	X	X		
Concomitant medications	X	X	X	X	X	X	X	X	X	X	X		
Targeted physical examination	X												
Laboratory Testing (Central Lab)													
Hematology		X				X		X	X			X	
Blood Chemistry		X				X		X	X			X	
Urinalysis		X										X	
Drug concentrations and Immunogenicity													
Drug concentration (PK) sample ¹⁰			X ¹⁰		X ¹⁰	X	X	X	X	X			
Immunogenicity (ADA) sample ¹¹			X ¹¹			X			X				
Pharmacogenomics (Optional)													
Whole Blood for DNA			X ²										

Visit Period	Screening/Baseline				Vaccine Response Assessment				Follow-Up			Unscheduled Visit	ET		
Study Day	-21 to 1				15	29 ¹	43	57	169	253	366				
	Screening	Pre-dose	Dose ¹	Post-Dose											
	Days After the First Vaccine Dose														
Window (day)					±2	-1 to +3	±2	±2	±7	±14	±14				

Table 5: Schedule of Events for Study Arms 9 and 6d (Enrollment Wave 4)

Visit Period	Screening/Baseline						Vaccine Response Assessment						Follow-Up			Unscheduled Visit	ET
	-21 to 1				7		15	29 ¹	43	57	169	253	366				
	Study Day	Screening	Pre-dose	Dose ¹	Post-Dose	Pre-dose	Dose ¹	Post-Dose	14	28	42	56	168	252	365		
Days After the First Vaccine Dose									±2	-1 to +3	±2	±2	±7	±14	±14		
Window (day)																	
Screening/Baseline and Key Laboratory Testing																	
Inclusion/exclusion	X	X															
Informed consent	X																
Informed consent for optional FBR sub-study ²	X																
Informed consent for optional PGx sub-study ²	X																
Medical history	X																
Demographics	X																
Height and weight	X																
Pregnancy test (WOCBP) ³	X ³	X ³				X ³				X ³						X	
SARS-CoV-2 rapid (local/POC) RT-PCR ⁴	X ⁴	X ⁴				X ⁴			X ⁴	X ⁴	X ⁴	X ⁴	X ⁴	X ⁴	X ⁴	X ⁴	
SARS-CoV-2 rapid serology ⁵	X ⁵	X ⁵															
SARS-CoV-2 serology (central lab) ⁵		X ⁵				X										X	
Enrollment Wave and Treatment Assignment																	
Site-managed assignment ⁶		X ⁶															
Randomization ⁶			X ⁶														
Study Drug and Vaccine Administration																	
REGN10933+REGN10987 (arm 9 only) ⁷								X ⁷									
Moderna mRNA-1273 vaccine (arms 9 and 6d) ⁷					X ⁷					X ⁷							
Biomarkers																	
Serum for SARS-CoV2 neutralization ⁸			X			X			X	X	X	X	X	X	X	X	X
Serum for serology characterization ⁸		X				X			X	X	X	X	X	X	X	X	X
Whole blood for PBMCs ⁸		X			X			X	X	X	X	X	X	X	X	X	X
Serum for exploratory research		X			X			X	X	X	X	X	X	X	X	X	X
Plasma for exploratory research		X			X			X	X	X	X	X	X	X	X	X	X
Safety																	
Vital signs ⁹	X	X ⁹		X ⁹	X ⁹		X ⁹		X ⁹								
Adverse events ¹²	X	X	X	X	X	X	X	X	X	X	X	X	X	X	X	X	
Concomitant medications	X	X	X	X	X	X	X	X	X	X	X	X	X	X	X	X	
Targeted physical examination	X																
Laboratory Testing (Central Lab)																	
Hematology			X			X				X		X	X			X	X
Blood Chemistry		X			X			X			X	X	X			X	X
Urinalysis			X														X
Drug concentrations and Immunogenicity																	
Drug concentration (PK) sample ¹⁰						X ¹⁰			X ¹⁰	X	X	X	X	X			
Immunogenicity (ADA) sample ¹¹						X ¹¹							X				
Pharmacogenomics (Optional)																	
Whole Blood for DNA			X ²														
Vaccine Booster Sub-Study (Optional)¹⁴																	

Visit Period	Screening/Baseline						Vaccine Response Assessment						Follow-Up			Unscheduled Visit	ET
	-21 to 1						7			15	29 ¹	43	57	169	253	366	
	Study Day	Screening	Pre-dose	Dose ¹	Post-Dose	Pre-dose	Dose ¹	Post-Dose	14	28	42	56	168	252	365		
Days After the First Vaccine Dose									±2	-1 to +3	±2	±2	±7	±14	±14		
Window (day)																	
Informed consent for vaccine booster sub-study ²						Refer to Table 6 .											
Sample collection and assessments																	

Table 6: Schedule of Events for the Moderna mRNA-1273 Vaccine Booster Sub-Study

Visit	Vaccine Booster Administration			Post-Booster Follow-Up
	Pre-Dose	Dose ¹	Post-Dose	
Visit Window	≥5 months after the second dose of the vaccine (primary series), and >35 days before end of the main study			28 days ±7 days after the vaccine booster
Informed consent for the booster sub-study ²	X			
Moderna mRNA-1273 vaccine booster shot		X		
Pregnancy test (WOCBP) ³	X			
SARS-CoV-2 rapid (local/POC) RT-PCR ⁴		X ⁴		X ⁴
Adverse events ¹²	X	X	X	X
Drug concentration (PK) sample ¹⁰	X			X
Serum for exploratory research	X			X
Plasma for exploratory research	X			X
Whole blood for PBMCs ⁸	X			X

9.1.1. Footnotes for the Schedules of Events

1. Throughout the study, study drug and/or vaccine administration will occur after all samples have been collected and all assessments have been performed.
2. Separate consent is required for participation in the optional vaccine booster sub-study (Section 9.2.10), optional future biomedical research sub-study (Section 9.2.8), and optional pharmacogenomics sub-study (Section 9.2.9). For subjects consenting to the genomics sub-study, the blood sample for genomic DNA should be collected at baseline (day 1) but may be collected at any visit.
3. All women of childbearing potential (WOCBP), with the exception of women with documented bilateral tubal ligation, will require pregnancy testing at screening, prior to study drug administration, and prior to COVID-19 vaccine administration. If a urine pregnancy test result is positive, a serum pregnancy test will be performed for confirmation. Subjects with confirmed pregnancy (by serum test) at screening will not be randomized. If the screening visit occurs on the same day as the baseline visit on day 1, pregnancy testing does not need to be repeated. Subjects with confirmed pregnancy at post-baseline dosing visits will be counseled according to Section 8.3.3.
4. If the screening visit occurs on the same day as the baseline visit on day 1, SARS-CoV-2-rapid RT-PCR test does not need to be repeated. Nasopharyngeal swabs will be used for rapid RT-PCR testing. Refer to Section 6.1.2 for more information on sample collection and visit scheduling for subjects with suspected COVID-19 or positive RT-PCR test result.

Post-baseline samples only: If the rapid RT-PCR test is positive at any time point post-baseline, the samples will be banked for viral sequencing.

Additional information is provided in Section 9.2.1.2.

5. If a rapid serology test is used at the screening visit, and screening occurs on the same day as the baseline visit, the rapid serology test does not need to be repeated at baseline. Additional information about the rapid serology test is provided in Section 9.2.1.3.

At screening, if the rapid serology test is not available locally, a rapid test may be performed at a central laboratory to determine eligibility, and a repeat of the test is not required at baseline.

6. Subjects will receive site-managed assignment (at screening) and randomized treatment assignment (at baseline on day 1) according to Section 8.5.
7. Note that not all subjects will receive study drug at randomization. Refer to Section 8.5 and Figure 1 for more information.

Study arms 4 and 5: Subjects assigned to study arms 4 and 5 will receive both the study drug and vaccine on day 1. The study drug will be administered first, followed by the vaccine. There must be a minimum of 2 hours waiting period between administration of the study drug and subsequent vaccine administration. Approximately 24 hours after completion of the study drug and vaccine administration on day 1, subjects will be followed up by telephone for safety. Subjects should be monitored for at least 1 hour after study drug or vaccine administration.

Study arms 6a, 6b, 6c, and 6d only: Subjects assigned to one of these study arms will not receive study drug. These subjects will receive the vaccine only. These subjects should be monitored for at least 30 minutes after vaccine administration.

Refer to Section 9.2.2 for additional information concerning administration and monitoring requirements following study drug and/or vaccine administration.

8. Serology characterization assays will be used to assess antibodies against various SARS-CoV-2 antigens including: S protein, RBD, S1, and N protein. Refer to Section 9.2.3.1, Section 9.2.3.2, and Section 9.2.3.3 for more information on procedures and assays related to vaccine response assessment.
9. Vital signs, including temperature, blood pressure, heart rate, and respiratory rate will be collected prior to and 30 minutes following each administration of the study drug or vaccine primary series (first and second dose) as described in Section 9.2.4.1.
10. Actual dosing time and drug concentration sample collection times will be recorded.

Study arms 1, 2, 3, 7, 8, and 9 (receiving IV infusion of study drug): At the indicated visit, blood for assessment of drug concentration in serum will be taken prior to dosing and within 60 minutes after the end of infusion (EOI). The EOI sample should be collected from the arm contralateral to that used for IV infusion. If not medically feasible, the EOI sample can be drawn from the same arm, but not from the infusion catheter.

Study arms 4 and 5 (receiving SC injection of study drug): At the screening/baseline visit, blood for assessment of drug concentration in serum will be taken prior to dosing. The post-dose blood collection should occur at least 1 hour after study drug administration.

Study arms 6a, 6b, 6c, and 6d (receiving no study drug): No blood for assessment of drug concentration in serum will be collected.

11. The window for pre-dose ADA sample collection should be as close to administration of study drug as is reasonable. Actual dosing time and ADA sample collection times will be recorded.
- Study arms 6a, 6b, 6c, and 6d (receiving no study drug):** No blood for ADA assessment will be collected.
12. Adverse events will be continuously monitored as described in Section 10.1.1.
13. **For Arms 1, 2, 3, 6a, 6c, 7 and 8:** For subjects receiving their COVID-19 vaccine booster as part of the sub-study, the vaccine booster may be administered at any time from 5 months after their second vaccine dose until study day 345. The *actual date* the subject received their second vaccine dose should be used (as opposed to using study day 43) to determine when the booster window should begin.
14. **For Arms 4, 5, 6b, 6d, and 9:** For subjects receiving their COVID-19 booster as part of the sub-study, the vaccine booster may be administered at any time from 5 months after their second vaccine dose until study day 331. The *actual date* the subject received their second vaccine dose should be used (as opposed to using study day 29) to determine when the booster window should begin.

9.1.2. Early Termination Visit

Subjects who are withdrawn from the study before the primary endpoint visit (56 days after the first dose of the vaccine; **day 71** for study arms 1, 2, 3, 6a, 7, 8, and 6c, and **day 57** for study arms 4, 5, 6b, 9, and 6d) will be asked to return to the clinic once for an **early termination (ET) visit** consisting of the end of study assessments (as described in the respective Schedules of Events).

9.1.3. Unscheduled Visits

All attempts should be made to keep subjects on the study schedule. Unscheduled visits may be necessary to repeat testing following abnormal laboratory results, for follow-up of AEs, or for any other reason, as warranted.

9.2. Study Procedures

9.2.1. Procedures Performed at the Screening/Baseline Visit

Procedures to be performed for the purpose of determining study eligibility or characterizing the baseline population include: medical history, demographics (including age, sex, race, weight, height), and SARS-CoV-2 RT-PCR and serology tests.

9.2.1.1. Informed Consent

Informed consent must be obtained according to the requirements described in Section 13.2. Additional informed consent must be obtained if subjects choose to participate in the optional vaccine booster sub-study (Section 9.2.10), optional future biomedical research sub-study (refer to Section 9.2.8), or optional pharmacogenomics sub-study (refer to Section 9.2.9).

9.2.1.2. SARS-CoV-2 Rapid RT-PCR

At screening, the investigator or designee will verify that the subject has tested negative for SARS-CoV-2 by a rapid RT-PCR test. Historical test results will not be accepted.

Subjects will also be tested for SARS-CoV-2 infection by the rapid RT-PCR test using nasopharyngeal (NP) swabs throughout the study according to the respective Schedules of Events. Any post-baseline virology samples that test positive for SARS-CoV-2 will be banked for viral sequencing Section 9.2.3.4.

9.2.1.3. SARS-CoV-2 Serology

The investigator or designee will verify that the subject has tested negative for circulating SARS-CoV-2-specific antibodies by a SARS-CoV-2 antibody test.

The diagnostic antibody test may be performed using a rapid lateral flow chromatographic immunoassay (LFIA) intended for the qualitative detection and differentiation of IgM and IgG antibodies to SARS-CoV-2. If the LFIA assay is not available locally, the rapid LFIA test at the central laboratory will be used to determine study eligibility.

9.2.2. Study Drug and Vaccine Administration and Post-Administration Monitoring

Refer to Section 8.5 for treatment assignments.

SC and IM Injection Administration

All subjects allocated to a SC regimen will receive either 4 (study arm 4) or 2 (study arm 5) injections of study drug on the day of administration. It is recommended that SC injection sites should be chosen among the different quadrants of the abdomen (avoiding navel and waist areas) and upper thighs. During study drug administration, each injection must be given in a different anatomical location (1 injection administered in the right lower quadrant of the abdomen, another in the left lower quadrant of the abdomen, etc).

All subjects will receive each Moderna mRNA-1273 vaccination dose through a single IM injection in the deltoid muscle ([CDC, 2021](#)).

Subjects should receive all doses of Moderna mRNA-1273 vaccine as assigned and as described in the EUA Fact Sheet ([Moderna COVID-19 Vaccine \[HCP Fact Sheet\], 2022](#)).

Study arms 4 and 5 only: Subjects will receive both study drug and vaccine on day 1. The study drug will be administered first, followed by the vaccine. There must be a minimum of 2 hours waiting period between administration of the study drug and subsequent vaccine. Administration of the individual regimens should be performed as described above.

Post-administration monitoring of study drug and vaccine

Study arms 1 through 5 and 7 through 9: Subjects should be monitored for at least 1 hour after study drug or vaccine administration. Vaccine recipients should be monitored for the occurrence of acute reactions according to the latest CDC guidelines ([CDC, 2021](#)). For study arms 4 and 5 (receiving study drug and vaccine on the same day), approximately 24 hours after completion of the study drug and vaccine administration on day 1, subjects will be followed up by telephone for safety.

Study arms 6a, 6b, 6c and 6d: Subjects assigned to each of these study arms will not receive study drug during this study. These subjects should be monitored for at least 30 minutes after vaccine administration.

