3.3.2. Risk-Benefit for Moderna mRNA-1273 Vaccine

Always refer to the latest EUA Fact Sheet ([Moderna COVID-19 Vaccine \[Patient Fact Sheet\], 2022](#)) . Information from the current version of the Fact Sheet (dated 07 January 2022) is provided below:

Benefit. In an ongoing clinical trial, Moderna mRNA-1273 vaccine has been shown to prevent COVID-19 following 2 doses given 1 month apart. The duration of protection against COVID-19 is currently unknown.

Risks.

There is a remote chance that the Moderna COVID-19 Vaccine could cause a severe allergic reaction. A severe allergic reaction would usually occur within a few minutes to one hour after getting a dose of the Moderna COVID-19 Vaccine. For this reason, the vaccination provider may ask the vaccine recipients to stay at the place where they received the vaccine for monitoring after vaccination. Signs of a severe allergic reaction can include:

- Difficulty breathing
- Swelling of face and throat
- A fast heartbeat
- A bad rash all over body
- Dizziness and weakness

Myocarditis (inflammation of the heart muscle) and pericarditis (inflammation of the lining outside the heart) have occurred in some people who have received the Moderna COVID-19 Vaccine, more commonly in males under 40 years of age than among females and older males. In most of these people, symptoms began within a few days following receipt of the second dose of the Moderna COVID-19 Vaccine. The chance of having this occur is very low. The vaccine recipients should seek medical attention right away if they have any of the following symptoms after receiving the Moderna COVID-19 Vaccine:

- Chest pain
- Shortness of breath
- Feelings of having a fast-beating, fluttering, or pounding heart

Side effects that have been reported in a clinical trial with the Moderna COVID-19 Vaccine include:

- Injection site reactions: pain, tenderness and swelling of the lymph nodes in the same arm of the injection, swelling (hardness), and redness

- General side effects: fatigue, headache, muscle pain, joint pain, chills, nausea and vomiting, fever and rash

Side effects that have been reported during post-authorization use of the Moderna COVID-19 Vaccine include:

- Severe allergic reactions
- Myocarditis (inflammation of the heart muscle)
- Pericarditis (inflammation of the lining outside the heart)
- Fainting in association with injection of the vaccine

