4.2. Secondary Endpoints

The secondary endpoints are:

- Absolute values, change from baseline, and percentage change from baseline in concentrations of vaccine-induced antibodies to the following SARS-CoV-2 antigens over time:
 - Anti-S protein
 - Anti-RBD
 - Other S protein subdomains (including S1, S2, and NTD)
- 50% inhibitory dilution (ID_{50}) titers of vaccine-induced neutralizing antibodies to SARS-CoV-2 S protein assessed over time after the first dose of Moderna mRNA-1273 vaccine

- Proportion of subjects with treatment-emergent adverse events (TEAEs) throughout the study
- Proportion of subjects with treatment-emergent serious adverse events (SAEs) throughout the study
- Proportion of subjects with infusion-related reactions (grade ≥ 2) to REGN10933+REGN10987 through day 4 post-infusion
- Proportion of subjects with injection site reactions (grade ≥ 3) to REGN10933+REGN10987 or each dose of Moderna mRNA-1273 vaccine through day 4 post-injection
- Proportion of subjects with hypersensitivity reactions (grade ≥ 2) to REGN10933+REGN10987 or each dose of Moderna mRNA-1273 vaccine through day 29 post-infusion or post-injection (as applicable)
- Concentrations of REGN10933 and REGN10987 in serum over time
- Immunogenicity, as measured by anti-drug antibodies (ADA) and neutralizing antibodies (NAb) to REGN10933 and REGN10987

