9.2.4. Safety Procedures

9.2.4.1. Vital Signs

Vital signs will include temperature, blood pressure, heart rate, and respiratory rate. Vital signs will be measured after the subject has been resting quietly for at least approximately 5 minutes and may be obtained in seated or supine position.

Vital signs will be collected prior to and approximately 30 minutes following each administration of the study drug or vaccine primary series (first and second vaccine dose). Vital signs may also be collected as needed, according to local standard of care and as per the discretion of the investigator.

Blood pressure measurements may be repeated once during screening.

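### The minimum on-site observation after a vaccine dose is 1 hour in every drug arm but 30 minutes in every control arm, so immediate vaccine reactions may be recorded less completely in controls

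*Protocol*

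**What the plan says.** Protocol 9.2.2 has two monitoring paragraphs. The one for the drug arms reads "Study arms 1 through 5 and 7 through 9: Subjects should be monitored for at least 1 hour after study drug or vaccine administration". The one for the controls opens "Study arms 6a, 6b, 6c and 6d: Subjects assigned to each of these study arms will not receive study drug during this study" and continues "These subjects should be monitored for at least 30 minutes after vaccine administration". Footnote 7 to the Schedules of Events (Protocol 9.1.1, reproduced in SAP 11.1) repeats the 30-minute minimum for 6a to 6d. It prints the 1-hour minimum under arms 4 and 5 only, and refers to 9.2.2 for further detail. Neither rule is limited to the primary series, and the booster sub-study text (Protocol 9.2.10, Table 6) gives no observation time of its own.

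On timing, Protocol 3.3.2 says "A severe allergic reaction would usually occur within a few minutes to one hour after getting a dose of the Moderna COVID-19 Vaccine".

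Protocol 4.2 makes two vaccine reactions secondary endpoints for each dose: hypersensitivity of grade 2 or higher through day 29, and injection-site reactions of grade 3 or higher through day 4. SAP 5.8.1 tabulates vaccine-related hypersensitivity, vaccine-related injection-site reactions and all vaccine-related TEAEs by treatment group. The trial is open-label (Protocol 8.6).

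Other ascertainment does not depend on arm. Under Protocol 9.2.4.1, "Vital signs will be collected prior to and approximately 30 minutes following each administration of the study drug or vaccine primary series". Subjects are told to telephone the site if their health changes (Protocol 6.1.1), and they are questioned about adverse events at each visit (Protocol 10.1.1).

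**The concern.** All arms receive the same vaccine, and reactions to it are compared by arm. The required period of direct observation nevertheless differs between exactly the groups being compared. If a reaction that starts after a control subject has left goes unrecorded, while the same reaction in a drug-arm subject is seen by staff, the drug arms look worse without any true difference. An excess produced in this way could be read as an interaction between antibody and vaccine, which is the question behind the secondary safety objective. Controls would also have less direct observation during the period the protocol itself names for severe allergic reaction.

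**Working it through.** The plan gives no figure to reproduce. The check is a comparison of the text, followed by a bound on size.

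**1. The minimums (Protocol 9.2.2; targets from Protocol 8.5, Table 2)**

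| | Drug arms 1-5, 7-9 | Control arms 6a-6d |
|---|---|---|
| Arms | 8 | 4 |
| Target subjects | 8 × 30 = 240 | 15 + 15 + 8 + 8 = 46 |
| Minimum per vaccine dose | 60 min | 30 min |
| Minimum over the two primary doses | 120 min | 60 min |

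The difference is 60 − 30 = 30 minutes per dose, and the ratio of the minimums is 60/30 = 2.0. Minutes 30 to 60 lie wholly inside the time frame in Protocol 3.3.2.

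**2. Does drug exposure explain the difference? (Table 2)**

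- Arms 1, 2, 3, 7 and 8: drug on day 1, vaccine on days 15 and 43, so 14 and 42 days after drug.
- Arms 4 and 5: drug on day 1, vaccine on days 1 and 29, so 0 and 28 days after drug.
- Arm 9: drug on day 7, vaccine on days 1 and 29, so 6 days before drug and 22 days after it.

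At every drug-arm dose except one, drug has already been given. The exception is dose 1 in arm 9. Its concurrent control, 6d, is vaccinated on the same study day, and neither arm has had drug, yet the minimums are 60 and 30 minutes. That is the clean case.

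**3. What can pick up a reaction after the subject leaves?**

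- Next scheduled visit after dose 1: 14 days later in waves 1 to 3 (day 15 to 29, or day 1 to 15) and 6 days later in wave 4 (day 1 to 7).
- Next scheduled visit after dose 2: 14 days later in all waves (day 43 to 57, or day 29 to 43).
- Next sub-study visit after a booster: 28 ± 7 days later.
- Questions at visits are open and do not name symptoms (Protocol 10.1.1). The schedules list no symptom diary.
- The instruction to telephone the site applies to everyone. Arms 4 and 5 also get a safety call about 24 hours after day 1 dosing that is not stated for 6b. This is a separate difference in the same direction.

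**4. Size, under stated assumptions**

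Let x be the share of immediate vaccine reactions starting 30 to 60 minutes after a dose, and m the share of those that controls never report later. Assume full recording in the drug arms, departure of controls at exactly 30 minutes, and no true difference. The apparent ratio for immediate reactions is then 1/(1 − x·m). The documents give neither x nor m.

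| | x = 10% | x = 30% |
|---|---|---|
| m = 1 (nothing reported later) | 1/0.90 = 1.11 | 1/0.70 = 1.43 |
| m = 0.5 | 1/0.95 = 1.05 | 1/0.85 = 1.18 |
| m = 0 (everything reported later) | 1.00 | 1.00 |

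For the secondary endpoint the ratio would be nearer 1, because the 29-day window also counts later events.

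For absolute numbers, Protocol 3.3.3 reports no hypersensitivity reactions among 54 + 99 = 153 subjects vaccinated in two other studies. As a rough guide only (the counts may include placebo recipients), the rule of three gives an upper bound of 3/153 = 2.0%. Applied to controls, 46 × 3/153 = 0.9 events per dose. A share of 10 to 30% of that is 0.09 to 0.27 events per dose, even if none were reported later.

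**The case against.** The strongest reply is that the difference is deliberate. Protocol 3.3.3 names a possible risk of hypersensitivity when antibody and vaccine are given close together and promises close monitoring. A reader might infer that at the second dose, when no arm is given study drug, the longer observation can only reflect assignment. The documents do not support that: dose 2 falls 22 to 42 days after drug, and the dose rationale in Protocol 3.2.2.2 rests on antibody persisting far longer. The two rules also do not contradict each other; they are arm-specific rules stated consistently.

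Nor would much be lost. Severe reactions are the least likely to go unreported, subjects are told to telephone the site, and grade 2 hypersensitivity already means that oral treatment is indicated (Protocol Table 8). Grade 3 injection-site reactions mean ulceration, necrosis or severe tissue damage, which do not depend on who is watching between minutes 30 and 60. No hypothesis is tested (Protocol 11.1).

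Most of this stands, and it limits the size. Two things remain. A reason to watch drug recipients longer does not make the by-arm comparison equal. It also cannot account for arm 9 at dose 1, before any drug.

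**Conclusion.** The point holds as a limited difference in ascertainment. The required minimum differs by arm at every vaccine dose, neither document equalises it, and the SAP does not allow for it. It bears on immediate vaccine-related hypersensitivity and on mild immediate vaccine-related TEAEs. Any effect would make the drug arms look worse. The primary ID50 endpoint and grade 3 or higher injection-site reactions are not plausibly affected.

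Two stronger readings should be resisted. A reader might infer that controls were in fact watched for half as long; both figures are minimums, and the documents do not give actual durations. A reader might also take a bias of 1.11 to 1.43 from the top row of the table; that row assumes both the timing of reactions and a complete absence of later reporting, and the call-in instruction and visit questioning speak against the latter. The size cannot be derived from the documents and is probably small. This is a cheap improvement, not a threat to the trial's conclusions.

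**What to change.** For remaining vaccinations, including sub-study boosters, reconcile the two paragraphs of Protocol 9.2.2 and footnote 7 (Protocol 9.1.1 and SAP 11.1) so that the minimum observation after a vaccine dose does not differ by arm. The length is for the sponsor's clinicians. SAP 2.1 describes randomization in the past tense, so this may do little for the primary series.

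For doses already given, add a table to SAP 5.8.1 of immediate vaccine reactions with onset in the first 30 minutes, the period that every arm's minimum covers. This needs onset clock times. Protocol 10.1.2 asks only for exact or estimated dates, while SAP 6.3 speaks of a start time, so availability must be checked first. If clock times were not captured, state the unequal observation as a limitation wherever vaccine reactions are compared by arm.

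The cost is a short text change, a somewhat different clinic stay in some arms, and one extra table or one sentence in the report.
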